9.5 Monitoring

The study team will monitor participant accrual to ensure the target number of evaluable participants is enrolled. Study sites will be required to report all participant dropouts and noncompliance, including missing PK sample times/visits to the study team as soon as they occur. The study team will make decisions on participant's replacement on conference calls or by emails.

During the study, the safety and tolerability of the study medications will be monitored by means of adverse events reports representing laboratory and clinical data, such as Toxicity Summary reports or Phase I/II reports provided by ACTG DMC. It is required for study sites to enter these data into the DMC database within a specified time period for data entry. The study team will discuss these reports on regularly scheduled conference calls or by email. It is the responsibility of the study team to interpret the adverse event data and make any decisions needed to protect study participants from undue risk. Any concerns will be presented to the DAIDS Clinical Representative.

9.6 Analyses

A detailed statistical analysis plan will be developed after protocol Version 1.0 is finalized and before the study is open to accrual. The following will provide a summary of analyses that will state key analysis approaches.

9.6.1 Analyses of Primary Outcome Measurements

The proportion of participants with sub-therapeutic MPA levels (<0.1 ng/mL) will be estimated based on the participants who complete the PK sampling at 12 weeks after DMPA administration. A 90% confidence interval (CI) will be provided for proportion using Clopper-Pearson exact method for binomial measurements. This CI will provide us reasonable evidence that the true proportion is greater than the threshold (6%), by determining whether the 90% CI is entirely above the threshold.

Individual-specific MPA concentration-time curves in the elimination phase will be estimated by fitting \log_e -linear regression models to the data of MPA concentrations obtained at time of maximum MPA concentration and later. These estimated individual elimination curves will then be used to estimate the times (weeks) where MPA concentration levels reach at 0.1 ng/mL. We will present descriptive statistics of these estimated weeks including mean, SD, median, interquartile range, minimum and maximum. Mixed-effects model analysis (allowing individual elimination slope to be both fixed and random variable) with repeated measurements within individual participants will also be performed to estimate the times for comparison purposes with the results obtained using the \log -linear regression models fitted for individual participants. These modeling approaches will provide the population mean estimate of the time where MPA concentration level reaches at 0.1 ng/mL with 90% CI, which will guide us to determine optimal dosing frequency of DMPA in the study population. Details of these modeling approaches will be described in the statistical analysis plan that will be generated separately and approved by study team.

Descriptive statistics of plasma progesterone levels will be tabulated by study week. If there are participants with progesterone levels >5 ng/mL, the proportion and percentage of participants with progesterone levels >5 ng/mL will be tabulated by study week.

Relationships of plasma progesterone levels with MPA concentration levels will be investigated by exploratory plots and using nonlinear regression models to better understand a lower limit of therapeutic MPA level that could prevent ovulation. This analysis will be based on MPA and plasma progesterone levels observed at week 10 and 12. If MPA clearance is truly induced by the coadministered drugs, MPA levels at these times may be low enough that plasma progesterone may have risen. We note that if plasma progesterone levels have not begun to rise by week 10/12, this analysis may have a poor statistical power.

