2.1.1 DMPA

Medroxyprogesterone acetate (MPA, Provera) is a 21-carbon synthetic progestin with high selectivity and activity resembling those of natural progesterone. MPA has been used extensively in combination with estrogens for oral hormone replacement therapy in postmenopausal women. Relative to progesterone, MPA undergoes substantially less first-pass hepatic metabolism when given orally. MPA has a plasma half-life of 24 hours, with hepatic metabolism to various polar compounds and their conjugates [1]. DMPA, given as a 150 mg intramuscular dose, inhibits ovulation for up to 14 weeks and is therefore, given every 3 months to ensure continuous contraception, with a typical use failure rate of 0.3% during the first year [15]. The apparent half-life of DMPA is approximately 50 days after the intramuscular (IM) injection. Peak plasma concentration (1 to 7 ng/mL) is reached within 3 weeks of the injection and decreases exponentially to become undetectable at 120 to 200 days after dosing. MPA levels stay above the concentration needed to suppress ovulation (0.1 ng/mL) for approximately 3 months [16, 17, 18]. MPA levels at 3 months (12 weeks, C_{min}) after injection ranges from 0.04 to 1.31 ng/mL and mean MPA C_{min} is 0.45 ng/mL with coefficient of variation (CV) of 53% when coadministered with NRTIs only and 0.37 ng/mL with CV of 57% when co-administered with EFV-containing regimen. Women may not ovulate for up to 6 months after the last DMPA dosing [19].

DMPA prevents conception by inhibiting gonadotropin release, leading to ovulation suppression and thinning of the endometrial lining. Luteal activity and ovulation, as indicated by a rise in serum progesterone to >5 ng/mL, occurs when the MPA concentration drops to <0.1 ng/mL [17, 20, 21].

DMPA is metabolized via the cytochrome p450 enzyme system [16] and induces the activity of CYP3A4. When given as an injectable, MPA induces activity of CYP3A4 by 25% [18]. PK studies of DMPA with selected antiretroviral agents have not demonstrated a reduced contraceptive efficacy as assessed through ovulation suppression measured by progesterone levels [16, 19]. Non-NRTIs

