9.2 Outcome Measures

9.2.1 Primary Outcome Measures

MPA concentration levels obtained at 2, 4, 6, 8, 10, and 12 weeks after DMPA is administered. The 12 week measurement will be the measurement obtained closest to 84 days after DMPA is administered. The allowable window for the measurement is ± 7 days, as stated in section 6.2.3.

Plasma progesterone levels obtained at 2, 4, 6, 8, 10, and 12 weeks after DMPA is administered.

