9.6.2 Analyses of Secondary Outcome Measurements

9.6.2.1 Estimation of MPA PKs in presence of EFV and RIF:

MPA PK parameters AUC_{0-12wk} , concentration at week 12 (trough concentration, C_{min}), C_{max} , CL/F , and $T_{1/2}$ will be estimated using non-

compartmental approach and descriptive statistics of these PK parameters will be presented. For the purpose of evaluating whether these PK parameters are significantly different from those in women not on the companion drugs, those PK parameters will be compared to those from the historic controls (A5093 Control Arm) using nonparametric two-sample Wilcoxon test. GMRs in MPA PK parameters of co-administration over administration-alone and associated 90% CIs will also be presented to provide magnitude of the differences as a supplementary analysis.

9.6.2.2 Estimation of time and variability in time to reach a MPA 0.1 ng/mL:

Times (weeks) and variability in times to reach MPA 0.1 ng/mL will be estimated using the analysis methods described in section 9.6.1.

9.6.2.3 Estimation of the proportion of participants reaching MPA level <0.1 ng/mL:

The proportion and percentage of participants with MPA concentration levels <0.1 ng/mL will be summarized by each of the study weeks 8 and 10. 90% CI for proportion at each week will be presented using Clopper-Pearson exact method.

9.6.2.4 Evaluation of toxicity and safety:

Signs and symptoms, chemistry and hematology with toxicity Grade ≥ 3 will be tabulated by study week.

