Statistical Analysis Plan

**ACTG A5338: An Open-Label, Non-Randomized Study of
Pharmacokinetic Interactions Among Depot Medroxyprogesterone Acetate
(DMPA), Rifampicin (RIF), and Efavirenz (EFV) in Women Co-Infected
with Human Immunodeficiency Virus (HIV) and Tuberculosis (TB)**

ClinicalTrials.gov Identifier: NCT02412436

**Version 1.0
November 28, 2018**

Introduction

This Statistical Analysis Plan addresses the following secondary objectives listed in the study protocol.

1.3.1. To estimate the area under the concentration-time curve (AUC), trough concentration (C_{\min}), maximum concentration (C_{\max}), apparent clearance (CL/F), and half-life ($t_{1/2}$) of MPA in HIV and TB coinfecting women taking EFV-based cART and RIF-containing TB treatment.

1.3.2. To estimate time and variability in time to MPA C_{\min} reaching 0.1 ng/mL or less in HIV and TB coinfecting women taking EFV-based cART and RIF-containing TB treatment.

Statistical Analysis Plan

- The concentration vs. time data for DMPA will be analyzed using nonlinear mixed-effects (NLME) modelling using the software NONMEM (version 7.4.2) (S. Beal, Sheiner, Boeckmann, & Bauer, 2009) pooling the data from the available studies A5338, A5238 and A5093.
- The modelling approach followed a stepwise procedure to first identify the structural model best describing the data, and then incorporate the effect of the study covariates such as weight, age, and effect of concomitant anti-retroviral and anti-tuberculosis treatment.
- Various structural pharmacokinetic models were evaluated, focusing on correctly characterizing the absorption after intra-muscular injection. The tested models included one and two compartments disposition, with first-order elimination and zero-, first-order, two parallel first order absorption.
- Model selection was based on changes in the NONMEM objective function value (Δ OFV), and visual inspection of conditional weighted residuals (CWRES) versus time, visual predictive checks, and basic goodness of fit plots (GOF).

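### The SD and range of separately fitted times to 0.1 ng/mL mix fit error with between-woman variation, and no model-based estimate is named for objective 1.3.2

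*Protocol*

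**What the plan says.** Protocol section 9.2.2.2 defines the outcome for objective 1.3.2 as the times at which individually fitted log-linear elimination slopes reach 0.1 ng/mL. Section 9.6.1 fits each line "to the data of MPA concentrations obtained at time of maximum MPA concentration and later" and then states: "We will present descriptive statistics of these estimated weeks including mean, SD, median, interquartile range, minimum and maximum". Section 9.6.2.2 refers back to it: "Times (weeks) and variability in times to reach MPA 0.1 ng/mL will be estimated using the analysis methods described in section 9.6.1".

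Section 9.6.1 also plans a mixed-effects model with random elimination slopes, which "will also be performed to estimate the times for comparison purposes with the results obtained using the" individual log-linear fits. The two approaches together are to give the population mean time with a 90% CI, "which will guide us to determine optimal dosing frequency of DMPA in the study population".

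The SAP lists objectives 1.3.1 and 1.3.2 as the ones it addresses and describes a nonlinear mixed-effects (NLME) analysis "pooling the data from the available studies A5338, A5238 and A5093". It does not mention the individual fits or the mixed model of section 9.6.1. Nor does it say how time to 0.1 ng/mL, or the variability of that time, comes out of the NLME model.

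For the individual fits, neither document sets a minimum number of points, a rule for flat or rising slopes, a rule for values below quantification, or a limit on extrapolation. Section 10.3 does cover values below quantification, but only for the NLME analysis.

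**The concern.** A fitted crossing time is a ratio with an estimated slope in the denominator. The SD of such times across women reflects two things: how much women truly differ, and how imprecisely each line is fitted. The first is what objective 1.3.2 asks for. The second depends on assay noise, sampling times and distance of extrapolation.

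Nothing in the individual-fit summary removes the second component. It is not small by design: six samples end at week 12, while most crossings are expected later. A shallow fitted slope sends the time far out, so the maximum suffers most.

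At stake is the description of how widely women differ in duration of coverage. An inflated SD makes the population look more heterogeneous than it is. A mixed or population model separates the two components, but the protocol gives its mixed model a comparison role and the SAP does not say that its NLME result replaces the section 9.6.1 statistics.

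**Working it through.** **Stated figures.** The documents give no figure for the SD or range of time to 0.1 ng/mL. The nearest is the week-12 design in section 9.4: n = 42, reject at 6 or more, 6% against 21%. Exact binomial calculation gives alpha 0.0382 and power 0.9009, so the stated 90% reproduces. The 90% Clopper-Pearson lower limit at 6/42 is 6.41%, above 6%.

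**How much is extrapolated.** The last scheduled sample is at week 12 (section 9.2.1: "MPA concentration levels obtained at 2, 4, 6, 8, 10, and 12 weeks after DMPA is administered"). If 6% to 21% are below 0.1 ng/mL by then, 100 − 21 = 79% to 100 − 6 = 94% cross later.

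A second route uses section 2.1.1: week-12 mean 0.37 ng/mL with EFV, CV 57%, apparent half-life 50 days. Assuming log-normality:
- Log SD = √ln(1 + 0.57²) = 0.530; log mean = ln 0.37 − 0.530²/2 = −1.135.
- Elimination rate k = ln 2/(50/7) = 0.0970 per week.
- Median crossing week = 12 + (log mean − ln 0.1)/k.

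| Fall in week-12 level | P(<0.1) at week 12 | Median crossing |
|---|---|---|
| none | 1.4% | week 24 |
| 30% | 6.3% | week 20 |
| 50% | 18.5% | week 17 |

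**Size of the fit error.** For a straight-line fit with residual log SD s, the approximate standard error of a crossing time T is (s/k)·√[1/n + (T − t̄)²/Sxx]. With all six samples (weeks 2 to 12), t̄ = 7 and Sxx = 70. Take k = 0.0970 and T = 20.4, the median crossing week after a 30% fall:
- s = 0.1: SE = 1.7 weeks.
- s = 0.2: (0.2/0.0970)·√(1/6 + 13.4²/70) = 3.4 weeks.
- s = 0.3: SE = 5.1 weeks.

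Adding these to a true SD near 6.5 to 6.8 weeks gives √(6.78² + 1.7²) = 7.0, √(6.52² + 3.4²) = 7.4 and √(6.69² + 5.1²) = 8.4. The ratios are 1.03, 1.13 and 1.26.

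**Simulation.** The formula ignores the skewness of a ratio, the choice of the observed maximum as starting point, and absorption. Trials of 42 women were therefore simulated with six samples each and a least-squares fit from the observed maximum. The week-12 mean was 0.37 × 0.7 = 0.259 ng/mL with CV 57%. The following are assumptions, not in the documents: residual log SD, slope CV of 20% or 40%, a 35-day alternative half-life, correlation 0.5 in size between slope and week-12 level, and the absorption phase. Results for slope CV 20%, in weeks:

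| Half-life, absorption | Residual SD | True SD | Fitted SD | Ratio | True / fitted range |
|---|---|---|---|---|---|
| 50 d, no | 0.1 | 6.78 | 7.03 | 1.04 | 31 / 32 |
| 50 d, no | 0.2 | 6.52 | 7.55 | 1.16 | 29 / 36 |
| 50 d, no | 0.3 | 6.69 | 9.30 | 1.39 | 29 / 46 |
| 50 d, yes | 0.1 | 6.75 | 8.10 | 1.20 | 30 / 34 |
| 50 d, yes | 0.2 | 6.82 | 9.51 | 1.39 | 29 / 49 |
| 50 d, yes | 0.3 | 6.70 | 11.43 | 1.71 | 29 / 57 |
| 35 d, no | 0.3 | 4.68 | 5.98 | 1.28 | 20 / 28 |
| 35 d, yes | 0.3 | 4.60 | 6.81 | 1.48 | 19 / 32 |

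Over all 24 scenarios the ratio ran from 0.98 to 1.71; at residual SD 0.1 it was 0.98 to 1.20. Further runs with half-lives of 30 to 50 days and half-life CV 20% to 35%, dropping fits with fewer than 3 points or a non-negative slope, gave 1.02 to 1.77. In filtered runs the IQR was inflated by only 6% to 19%. The median moved by between +0.6 weeks (17.9 to 18.5) and −2.4 weeks (20.0 to 17.6) across the 24 scenarios.

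**The obvious substitute.** The SD of the mixed model's individual (shrunken) estimates was 0.59 to 1.07 times the truth, so it usually understates.

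**The case against.** The strongest reply is that the documents already contain the right tool. The SAP assigns 1.3.2 to an NLME model, section 10.1.3 sets out to separate between-subject from unexplained variability, and section 10.3 extracts time above the target concentration. Section 9.6.1 defers modelling details to the SAP. This stands in part: no new model is needed, and the gap is one of derivation and precedence. It does not close the point, because the protocol still defines the outcome by individual fits and promises their SD, minimum and maximum, while the SAP promises no SD of time.

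A second reply is that the size is not fixed by the documents. That is correct. Residual error and slope variability are assumed, and with small residual error the inflation is negligible. Section 9.6.1 also already reports the median and IQR, which hold up much better. Late peaks are a minor issue, since section 2.1.1 says: "Peak plasma concentration (1 to 7 ng/mL) is reached within 3 weeks of the injection".

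A reader might infer that the 90% CI for the mean time is therefore too wide. The plan does not support that. The variance of a mean of estimated times is (between-woman variance + fit variance)/n, so fit error belongs in that interval. In simulation, nominal 90% intervals covered 84% to 91% without an absorption phase and 69% to 91% with one, so they were never materially conservative.

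A reader might also infer that dosing frequency rests on the individual fits alone. It does not: section 9.6.1 draws the mean and CI from both approaches, and section 10.4 adds simulation from the population model.

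**Conclusion.** The point holds as a secondary-objective reporting problem. The SD and range promised for variability in time contain fit error, and on the plan's 6% to 21% proportions about 79% to 94% of the times are extrapolated. The share would be smaller if induction were much stronger than planned.

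The SD tends to be overstated by a factor of about 1.0 to 1.8 for residual log SD 0.1 to 0.3 and half-lives of 30 to 50 days. The factor is between negligible and about 1.2 at residual SD 0.1. The maximum is inflated more; the median and IQR much less. A doubling of the SD was not reproduced in these runs.

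The sized primary analysis, the week-12 proportion below 0.1 ng/mL, is unaffected.

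**What to change.** State in the SAP that the estimate for objective 1.3.2 is the between-woman SD and percentiles of time to 0.1 ng/mL implied by the fixed effects and variance components of one named model, either the section 9.6.1 mixed model or the NLME model. They can be obtained by simulating women from the fitted model. Say which model takes precedence, and that the SD of shrunken individual estimates will not be used.

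Keep the individual fits as a descriptive display: median and IQR only, with at least 3 post-peak points and a negative slope required, a stated rule for values below quantification, and the number of women excluded.

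An interval-censored curve of time to the first value below 0.1 ng/mL is optional. Most women would be right-censored, so it would say little about variability.

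The cost is SAP wording and light programming, since both models are already planned. The downside is reliance on the assumed random-effects distribution. For example, a normally distributed slope leaves some probability near zero, which can dominate an implied SD; the percentiles are less sensitive to this and should be reported beside it.

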1.2 Primary Objectives

- 1.2.1 To estimate the optimal dosing frequency of depot MPA (DMPA) for HIV and TB coinfecting women taking EFV-based combination antiretroviral therapy (cART) and RIF-containing TB treatment based on a target MPA concentration >0.1 ng/mL.
- 1.2.2 To determine whether a 150 mg DMPA IM injection will be adequate to suppress ovulation through 12 weeks in women taking EFV-based cART and RIF-containing TB treatment based on serial plasma progesterone concentrations.

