1.3 Secondary Objectives

- 1.3.1. To estimate the area under the concentration-time curve (AUC), trough concentration (C_{\min}), maximum concentration (C_{\max}), apparent clearance (CL/F), and half-life ($t_{1/2}$) of MPA in HIV and TB coinfecting women taking EFV-based cART and RIF-containing TB treatment.
- 1.3.2. To estimate time and variability in time to MPA C_{\min} reaching 0.1ng/mL or less in HIV and TB coinfecting women taking EFV-based cART and RIF-containing TB treatment.
- 1.3.3. To estimate the proportion of participants who maintain MPA levels above the minimum level thought to suppress ovulation (MPA 0.1ng/mL) through 12 weeks after DMPA administration.
- 1.3.4. To evaluate the toxicity and safety of concurrent RIF, EFV, and DMPA use.

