9.2.2 Secondary Outcome Measures

9.2.2.1 Estimation of MPA PK parameters in HIV and TB co-infected women taking EFV and RIF:

MPA PK parameters AUC over the 12 weeks (AUC_{0-12wk}), C_{min} , C_{max} , apparent clearance (CL/F), and half-life ($t_{1/2}$) calculated using standard non-compartmental method: These PK parameters will be calculated based on the MPA concentrations obtained every 2 weeks over the 12 weeks. MPA concentration obtained at entry (prior to DMPA administration) will be evaluated as confirmation that no DMPA was taken prior to study entry.

9.2.2.2 Estimation of time and variability in time to reach MPA 0.1 ng/mL:

Times (weeks) where elimination slopes estimated fitting \log_e -linear regression models to the individual MPA concentrations obtained in the elimination phase reach MPA level of 0.1 ng/mL: The exact sampling time (weeks) will be used.

9.2.2.3 Estimation of the proportion of participants reaching MPA level <0.1 ng/mL at specified time points:

MPA concentration levels obtained at study weeks 6, 8, and 10. Since the week 12 measurements will be evaluated as the primary outcomes (section 9.2.1), the MPA measurements at study weeks 6, 8, and 10 after DMPA administration will be studied for any earlier sign of MPA levels <0.1 ng/mL.

9.2.2.4 Evaluation of toxicity and safety:

All adverse events with toxicity Grade ≥ 3 from signs/symptoms and chemistry and hematology laboratory analyses.

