9.4 Sample Size and Accrual

It is known that DMPA, EFV, and RIF drugs share some common metabolic pathways via the CYP3A4 enzyme system: MPA is metabolized by and induces CYP3A4 activity; RIF is primarily metabolized by CYP2B6 system but also by CYP3A4 and induces CYP3A4 and CYP2B6 enzyme activities; EFV is primarily metabolized by CYP2B6 and both induces and inhibits CYP3A4 enzyme activity (mixed and unpredictable activity). Therefore, it is anticipated that co-administration with EFV and RIF will induce clearance of MPA concentration, resulting in lower MPA concentrations during the elimination phase, compared to those seen when DMPA is administered alone. Thus, DMPA may need to be administered more frequently when used together with EFV and RIF.

The study hypothesis is that concurrent use of EFV and RIF increases the clearance of MPA, resulting in reduced MPA concentrations. The study will evaluate whether more frequent DMPA dosing is needed when DMPA is administered in combination with EFV and RIF in HIV- and TB-infected women. The evaluation of dosing frequency will be conducted by estimating the proportion of women with MPA levels <0.1 ng/mL 12 weeks post-dose (at the end of the dosing cycle). The critical value 0.1 ng/mL for MPA levels was chosen based on published papers including studies by Mishell [17] and Smit et al. [55]. These studies indicate that when MPA level falls below 0.1 ng/mL, serum progesterone level rises and the probability of ovulation increases.

In ACTG DMPA studies A5093 and A5283 in HIV-infected women, of the 79 PK evaluable participants, 5 women had MPA levels <0.1 ng/mL at 12 weeks after a single dose of DMPA was administered. None of these 5 women, however, had any evidence of ovulation (serum progesterone levels remained below 5 ng/mL). In a study by Smit et al. [56] in 94 women, all but one woman had MPA levels above 0.1 ng/mL at 12 weeks after DMPA administration. These 94 women had received either a single dose or multiple doses of DMPA. Therefore, based on the single dose studies, the proportion of women with MPA levels <0.1 ng/mL (sub-therapeutic MPA levels) 12 weeks post-dose is thought to be about 6% in normal DMPA use, although a study conducted by Trussell [57] showed that there is a contraceptive failure rate of about 0.3% when DMPA is used correctly.

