The primary analysis outcome will be the proportion of women with sub-therapeutic MPA levels (<0.1 ng/mL) at 12 weeks. A one-sided binomial test with significance level 0.05 will be used to test the null hypothesis that the proportion of women with sub-therapeutic MPA level is 6% or less. A sample size of 42 women provides 90% power to reject the null hypothesis if the proportion of women with sub-therapeutic MPA levels in this study is at least 21% (this is 15% or higher increase from the 6% threshold). With a sample size of 42 women, the underlying true proportion will be declared as statistically significant increase if 6 or more women have sub-therapeutic MPA levels at 12 weeks (this is equivalent to saying that 90% CI for the underlying proportion is entirely above the 6% threshold). Based on the results from a PK study of oral contraceptives containing ethinyl estradiol (estrogen) and norethindrone (progestin) which are metabolized by CYP3A4 enzyme [58], the study team considers that the underlying proportion of women with sub-therapeutic MPA levels of 21% or higher (15% or higher

increase from the 6% threshold) is plausible in the setting of coadministration with EFV and RIF.

The statistical power was also examined to see if the sample size will achieve a plausible power to detect a clinically meaningful decrease (30%) in MPA concentration at 12 weeks (MPA C_{min}) as one of the secondary objectives. With a significance level of 0.05, a one-sided t-test showed about 91% and 84% power to detect a 30% decline when the coefficient of variation (CV) is 60% and 70%, respectively (in the ACTG study A5093, CV of MPA C_{min} was approximately 57% when coadministered with EFV). We note that this power was examined in \log_e -scale since it is known that PK parameter C_{min} has a \log -normal distribution.

To protect against 10% loss of the primary outcomes after study accrual is closed, the study will enroll a total of 46 women. (In the ACTG DMPA study, A5093, the loss of the primary outcomes of week 12 was 9.8% [6 of 61 participants] due to either sample specimen loss or assay results not available.)

A participant is considered to be evaluable for the primary objective if the participant completes the MPA PK sampling during the study period of 12 weeks after DMPA administration. The participant replacement criteria are described in sections 8.1 and 8.2.

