10.0 PHARMACOLOGY PLAN

Women stable on an EFV and 2 NRTIs-based regimens, who are on RIF and INH, and who have not received DMPA within the last 180 days, will receive one dose of DMPA at

study entry. An optional dose of DMPA will be available at no cost to all study participants, after all week 12 study evaluations are completed. Refer to section 5.1.1 for the allowed NRTIs and section 5.4.2 for the prohibited NRTI combinations.

The primary PK analysis is described in section 9.6. The secondary PK analysis employing a population approach and nonlinear mixed effects modelling is described in this section.

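### The primary analysis takes the mean time to 0.1 ng/mL as its guide to dosing frequency, but about half the women are below target by then; the proportion-matched time planned in Section 10 fits the objective better

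*Protocol*

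**What the plan says.** Objective 1.2.1 (Protocol Section 1.2) reads "To estimate the optimal dosing frequency of depot MPA (DMPA", and it rests on a target MPA concentration above 0.1 ng/mL.

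Three parts of the protocol bear on how that frequency is reached.

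- **Section 9.4** states: "The primary analysis outcome will be the proportion of women with sub-therapeutic MPA levels (<0.1 ng/mL) at 12 weeks". It also states: "The evaluation of dosing frequency will be conducted by estimating the proportion of women with MPA levels <0.1 ng/mL 12 weeks post-dose". The reference is 6%, taken from 5 of 79 women in earlier single-dose studies.
- **Section 9.6.1** fits log-linear elimination curves to each woman and a mixed-effects model across women. It then gives a "population mean estimate of the time where MPA concentration level reaches at 0.1 ng/mL with 90% CI, which will guide us to determine optimal" (that is, dosing frequency). The SD, median, interquartile range and extremes of the individual times are listed as descriptive statistics.
- **Section 10** plans to predict when the share of women under the threshold equals the historical week-12 share (10.1.4 and 10.3). Section 10.4 ties optimal dosing frequency to a target proportion of women, without giving a number. Section 10.0 labels this work: "The secondary PK analysis employing a population approach and nonlinear mixed effects modelling is described in this section".

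Time to 0.1 ng/mL is itself a secondary objective (1.3.2, "To estimate time and variability in time to MPA") and a secondary outcome (9.2.2.2, "Estimation of time and variability in time to reach MPA 0.1 ng/mL"). Section 9.6.2.2 sends its analysis back to the primary section: "Times (weeks) and variability in times to reach MPA 0.1 ng/mL will be estimated using the analysis methods described in section 9.6.1".

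The SAP covers only secondary objectives 1.3.1 and 1.3.2. It describes no proportion-matched time and no dosing simulation.

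**The concern.** The protocol judges adequacy by the proportion of women below 0.1 ng/mL, with 6% as the level expected in ordinary use. The mean crossing time is not on that scale. It marks the point by which roughly half the women have crossed, whatever proportion is regarded as acceptable. Its confidence interval narrows as the sample grows and says nothing about the spread between women.

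The week-12 test does not fill the gap. It can show whether week 12 has an excess over 6%, but it yields no time, and a dosing frequency requires one. Within 9.6.1 the mean is the only time statistic given a guiding role. A reader who takes it at face value is pointed to a time when about half the women are below target.

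**Working it through.** **Inputs from the protocol.** Null proportion 6%, alternative 21%, n = 42, rejection at 6 or more (9.4). CV of week-12 MPA with efavirenz 57% (2.1.1, 9.4). Log-normal Cmin (9.4). Apparent half-life about 50 days (2.1.1). Latest permitted sample 84 + 7 = 91 days, or week 13 (9.2.1).

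**Assumed.** Half-lives of 35 and 25 days, to represent induced clearance, and all between-woman slope variation.

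**1. The protocol's own figure.** The exact binomial with rejection at 6 or more of 42 gives one-sided alpha 0.0382 at 6% and power 0.9009 at 21%, so the stated 90% reproduces. The Clopper-Pearson 90% lower limit is 6.4% for 6/42 and 4.8% for 5/42, which agrees with the stated rule.

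**2. Common elimination slope.** Log SD = sqrt(ln(1 + 0.57²)) = 0.530, and k = ln 2 / half-life. If a proportion p is below 0.1 ng/mL at week 12:

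- mean crossing time = 12 + z(1-p) × 0.530/k
- time when 6% are below = mean − 1.555 × 0.530/k

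For a 50-day half-life, 0.530/k = 38.3 days = 5.47 weeks. With p = 21%, z = 0.806, so the mean is 12 + 0.806 × 5.47 = week 16.4 and the 6% time is 16.4 − 1.555 × 5.47 = week 7.9.

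| Half-life (days) | Mean time, 21% below at week 12 | Time when 6% are below | Mean time, 6% below at week 12 |
|---|---|---|---|
| 50 | week 16.4 | week 7.9 | week 20.5 |
| 35 | week 15.1 | week 9.1 | week 17.9 |
| 25 | week 14.2 | week 10.0 | week 16.2 |

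Crossing times are symmetric here, so exactly 50% of women are below target at the mean.

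**3. Slopes that differ between women.** Both cases take 21% below at week 12.

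- Slope CV 30%, independent of the week-12 level: means at week 16.8/15.4/14.4 and 6% times at week 7.7/9.0/9.8 (half-life 50/35/25 days). At the mean, 53% are below.
- Slopes acting from a week-3 peak, week-12 log SD held at 0.530: with CV 20%, means at week 16.9/15.5/14.6, 6% times at 8.2/9.4/10.2, and 53-54% below. With CV 30%, means at 17.6/16.0/14.9, 6% times at 8.5/9.6/10.2, and 56% below.

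The share exceeds one half because crossing times become right-skewed. A separate simulation over wider assumptions (half-life 20-50 days, slope CV up to 50%, concentration CV 30-70%) gave mean times at week 13.5-20.4 with 50-60% below, and 6% times at week 7.1-10.6. Reading the time from the population-typical curve instead of averaging individual times gave 50-53% below.

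**4. Extrapolation.** In all the models of steps 2 and 3, 67-73% of crossing times lie beyond week 13. The mean therefore rests largely on times past the last sample.

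**5. Even at the reference.** With exactly 6% below at week 12, the mean falls at week 16.2-20.5 with a common slope and as late as week 22.2 with varying slopes.

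**6. What the alternative costs in precision.** With 42 women, 21% below and a common slope, the 90% half-width is 1.0/1.5/2.1 weeks for the 6% time and 0.7/1.0/1.4 weeks for the mean (half-life 25/35/50 days), a ratio of about 1.5. The reference is uncertain too: 5/79 has an exact 90% CI of 2.5-12.8%, which moves the matched time over 5.7-10.2, 7.6-10.7 and 8.9-11.1 weeks (half-life 50/35/25 days).

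**The case against.** The strongest reply is that the remedy is already in the protocol. Section 10.4 links dosing frequency to a target proportion, Section 3.0 promises modelling for the same purpose, and Section 9.4 evaluates dosing frequency by the week-12 proportion. A reader would also see the spread of individual times, and proportions at weeks 8 and 10 with exact 90% CIs, close to where the 6% times fall. To guide is not a decision rule. This stands in part: what is missing is precedence and a link, not a calculation. But the week-specific proportions give no time, and 9.6.1, where the primary objective is analysed, gives that role to the mean.

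A second reply is that the illustrative weeks are loosely anchored. A log-normal distribution with the protocol's mean of 0.37 ng/mL and CV of 57% puts only 1.4% below 0.1 ng/mL; reaching 6% needs a mean of about 0.26 ng/mL. That is fair. It weakens the particular weeks, which are conditional on the protocol's own 6% and 21%, but not the share below target at the mean.

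A third is that the protocol also assesses contraception by progesterone, and none of the five historical women below 0.1 ng/mL showed evidence of ovulation. Objective 1.2.1, however, is defined on MPA alone; progesterone belongs to 1.2.2.

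A fourth is that the matched time depends on 5/79 and the mean does not. This stands: the factor of 1.5 understates the total uncertainty, and a sensitivity range is needed.

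**Conclusion.** The concern holds. Section 9.6.1 guides a primary objective with a statistic at which 50-56% of women are below target in the main models (up to 60% under wider assumptions), roughly eight to nine times the 6% reference (50/6 = 8.3; 56/6 = 9.3). At the 21% alternative, the mean and the 6% time differ by about 4 weeks at a 25-day half-life (14.2 − 10.0) and about 9 weeks at 50 days with varying slopes (17.6 − 8.5).

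That about half the women are below target at the mean needs no particular half-life. The weeks do depend on log-linear decline, the 57% CV, the assumed half-lives and the assumed slope variation.

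The two summaries describe one distribution, so this is a poor choice of guide, not a contradiction between formal conclusions. It does not affect the primary test, sample size or data collection.

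**What to change.** - In Section 9.6.1, replace the mean as the guide for objective 1.2.1 with the time at which the model-predicted proportion below 0.1 ng/mL equals the historical week-12 proportion.
- Report it with a 90% CI, and with a sensitivity range using 2.5% and 12.8% as the reference in place of 6%.
- Keep the mean and median times as description, and flag crossing times extrapolated beyond the last sample.
- Reconcile Sections 9.4, 9.6.1, 10.1.4, 10.3 and 10.4: say which statistic prevails, give the target proportion in 10.4 a number, and resolve the threshold unit, printed as ng/L in 10.1.4 and 10.3 but ng/mL elsewhere.
- Carry the matched time into the SAP.

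This is a change of estimand and proposes no dosing interval. The cost is wording in the protocol and SAP; the modelling is already planned and no new data are needed. The price is a less precise, more model-dependent estimate: about 1.5 times the interval width from sampling alone, plus the uncertainty in 5/79.
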